7.4 PRIMARY ENDPOINT(S)

No primary efficacy endpoint is defined for this trial.

Analysis of the primary safety endpoint, i.e. proportion of patients with ocular adverse events over the on-treatment period, is provided in [Section 7.8](#).

7.5 SECONDARY ENDPOINT(S)

Analyses of the secondary safety endpoint, i.e. proportion of patients with adverse events other than ocular adverse events over the on-treatment period, are described in [Section 7.8](#).

7.5.1 Key secondary endpoint(s)

This section is not applicable as no key secondary endpoints are defined for this trial.

7.5.2 Secondary endpoint(s)

[figure not shown]
The frequency and percentage of patients in the FAS with at least 2 steps improvement from baseline on the DRSS, as defined in [Table 5.2.2: 1](#), in the study eye at week 12 will be summarized by treatment. Baseline DRSS is the value recorded at Visit 2a. If DRSS is not

Proprietary confidential information © 2020 Boehringer Ingelheim International GmbH or one or more of its affiliated companies

[figure not shown]
measured at Visit 2a, baseline DRSS is the value recorded at Visit 1. The frequency of patients reporting improvement in DRSS of at least 2 steps is expected to be low. The risk difference and corresponding 95% confidence intervals calculated using the method of Chan and Zhang ([7](#)) will be reported.

[figure not shown]
In addition, a shift table showing the frequency and percentage of patients reporting each Week 12 DRSS by baseline DRSS value will be presented. A visual display of the percentage of patients experiencing no change from baseline, a one-step and two-step improvement in DRSS from baseline to Week 12 or one-step worsening will be created. Similar summaries will be prepared using DRSS data collected from the non-study eye.

[figure not shown]
If a sufficient number of patients report improvement of 2 steps or more in the study eye, logistic regression analyses adjusted for visit, treatment and baseline visual acuity will be performed as exploratory analyses. The resulting odds ratios at each time point and corresponding 95% confidence interval will be presented, if modeling is possible.

Additionally, analyses described in this section will be repeated using the PPS instead of the FAS.

7.7 EXTENT OF EXPOSURE

Basis for the assessment of treatment exposure will be the amount of trial medication and the duration of exposure in days calculated across the on-treatment period for each patient.

Standard summary statistics will be displayed by treatment arm. In addition, the number and percentage of patients in exposure categories defined as 0 to 6 weeks, >6 to 12 weeks will be summarized.

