This interim phone call will be performed in advance to the EOT visit in order to collect AEs, changes in concomitant therapy, and to check handling of the trial drug diary. Patients should be reminded not to take medication in the morning prior to the EOT visit.

End of Treatment (EOT) Visit:

For patients who complete treatment as scheduled, the day of the EOT Visit is the last day of treatment where trial drug will be administered at the site from the kit that the patient returns to the site.

The overall duration of the anticipated treatment period (Randomization to EOT) should not be less than 84 days; therefore the EOT visit is scheduled at Day 85 with a time interval of up to +6 days at maximum.

If the trial drug intake needs to be permanently stopped during the treatment period for any reason prior to the scheduled EOT visit, including that patients are not willing to continue trial drug intake any longer, the EOT visit will be completed instead of the planned treatment period visit as soon as possible after trial drug discontinuation. In this case the patient should be asked to further attend to the follow-up visits and assessments until the end of the trial unless they withdraw consent to participate in the trial. It is important to distinguish between premature trial drug discontinuation, i.e. early discontinuation, and complete withdrawal of consent to participate in further study procedures.

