6. GENERAL ANALYSIS DEFINITIONS

6.1 TREATMENT(S)

Treatments used in this trial are described in [Table 6.1:1](#). For basic information on treatments to be administered in this trial and the assignment of treatment arm, see CTP Section 4.

Table 6.1: 1 Treatment descriptions

Long Name	Short Name
Placebo	Placebo
BI 1467335 10 mg QD	10 mg QD

The trial periods defined in [Table 6.1:2](#) will be used for analysis of trial data.

Table 6.1: 2 Trial periods

Trial Period	Start time	Stop time
Screening	Date of informed consent	Date of first treatment administration (Visit 2a) – 1 day
On-treatment (treatment period + residual effect period)	Date of first treatment administration (Visit 2a)	Date of individual patient's end of trial participation

For this trial, the residual effect period (REP), as defined in the CTP Section 5.2.6.2, is considered the entire period from the date of last administration of trial medication until the individual patient's end of trial date. The statistical analysis and reporting of treatment-emergent adverse events will include all adverse events occurring or worsening during the on-treatment period which includes residual effect period (REP).

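### SAP 7.7 measures exposure over a period that includes the 12-week drug-free follow-up, and its categories have no level for the scheduled last dose on Day 85 to 91

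*SAP*

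**What the plan says.** SAP 7.7 rests exposure on the quantity of study drug and on "the duration of exposure in days calculated across the on-treatment period for each patient". It promises two displays. The first is general: "Standard summary statistics will be displayed by treatment arm". The second is an added count of patients in "exposure categories defined as 0 to 6 weeks, >6 to 12 weeks". The section gives no first-to-last-dose formula, no day-count rule and no level above 12 weeks.

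The on-treatment period is a defined term. SAP Table 6.1: 2 makes it the treatment period plus the residual effect period, starting at first administration and stopping at "Date of individual patient's end of trial participation". The text below the table says that the residual effect period "is considered the entire period from the date of last administration of trial medication until the individual patient's end of trial date". SAP 5.1 gives the length of the on-treatment period as 24 weeks.

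SAP 7.3 uses the term differently. For compliance, the on-treatment period is divided into 28-day intervals that end at Visits 3, 4 and EOT, which is dosing time only.

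Protocol 6.2.2 sets a minimum treatment duration of 84 days and continues: "therefore the EOT visit is scheduled at Day 85 with a time interval of up to +6 days at maximum". The same section makes the EOT day the last dosing day for a patient who completes as scheduled. Protocol 6.2.3 places the last follow-up visit (FU3) 12 weeks after the last intake.

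**The concern.** A long residual effect period is a reasonable rule for attributing adverse events to a drug that binds its target irreversibly. It does not measure how long patients took the drug. If a programmer applies Table 6.1: 2 to SAP 7.7 as written, the report will give completers about twice the treatment duration that they had.

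Separately, the categories stop at the nominal 12 weeks, while the schedule puts the last dose on or just after that boundary. The patients who received the full planned course are then the ones without a category. The main objective is the safety and tolerability of 12 weeks of treatment, so a reader will look to the exposure table to see how many patients in each arm received that course.

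**Working it through.** **Inputs**
- First dose is Day 1 and there is no Day 0 (SAP 6.7).
- Scheduled last dose is at EOT, Day 85 to 91 (Protocol 6.2.2; Flow Chart window +6).
- FU3 is at last dose + 84 days, window ±6 (Protocol 6.2.3; Flow Chart).
- The top category bound is 12 weeks = 12 × 7 = 84 days (SAP 7.7).

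**The plan's own figure.** For EOT on Day 85 and FU3 on schedule, the on-treatment period ends on Day 85 + 84 = Day 169. Elapsed time is 169 − 1 = 168 days, and 168 / 7 = 24.0 weeks, which reproduces the 24 weeks in SAP 5.1. Counted inclusively it is 169 days, and 169 / 7 = 24.1 weeks. The off-drug share is 84 / 169 = 49.7%, and the ratio to inclusive dosing days is 169 / 85 = 1.99.

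**A scheduled completer under each reading**

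| Period | Day count | Formula | Range | Fits the top category (≤ 84 days)? |
|---|---|---|---|---|
| On-treatment, Table 6.1: 2 | inclusive | EOT day + 84 ± 6 | 163 to 181 days (23.3 to 25.9 weeks) | none |
| On-treatment, Table 6.1: 2 | elapsed | EOT day + 84 ± 6 − 1 | 162 to 180 days (23.1 to 25.7 weeks) | none |
| Dosing only | inclusive | EOT day | 85 to 91 days (12.14 to 13.0 weeks) | none |
| Dosing only | elapsed | EOT day − 1 | 84 to 90 days (12.0 to 12.86 weeks) | only EOT on Day 85 |

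**Early stoppers under the literal definition.** A patient whose last dose is on Day 2 and who attends FU3 on schedule has 2 + 84 = 86 days inclusive (85 elapsed), already above 84. The two categories would then hold almost only patients who left the trial early, whatever their dosing.

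**Does correcting the period alone suffice?** No. The two dosing-only rows still leave out all scheduled completers, or all but those seen exactly on Day 85. The categories need a further level as well.

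**The case against.** The strongest reply is that the authors meant dosing time. SAP 7.7 pairs duration with the quantity of drug, a 12-week upper bound makes sense only for dosing, and SAP 7.3 uses the term that way. The phrase can also be read as days of exposure falling within the on-treatment period, not the length of that period. This has force: the doubling depends on taking the defined term at its word. But Table 6.1: 2 states that its periods are for the analysis of the trial data, and SAP 7.7 offers no formula to displace it. A term used in two senses leaves the programmer to guess. The reply also leaves the category problem in place.

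Three stronger readings are tempting, and the documents do not support them.
- A reader might infer that no completer fits a category on any count. The protocol itself equates Day 1 to Day 85 with 12 weeks and derives Day 85 from an 84-day minimum, which is elapsed counting. On that count, with dosing days only, a completer seen exactly on Day 85 fits.
- A reader might infer that completers vanish from the exposure report. They do not: the summary statistics cover all patients, and the categories are an addition.
- A reader might infer that adverse event results are distorted because exposure is their denominator. SAP 7.8.1 counts patients with events, in the treated set. No exposure-adjusted rate appears in the published text.

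**Conclusion.** The point holds as a fault in the descriptive exposure report. Followed literally, SAP 7.7 gives a scheduled completer 169 days in place of 85 (163 to 181 across the visit windows), and the summary statistics carry that inflation. The categories cannot hold the scheduled course: no completer fits under three of the four readings, and under the fourth only those with EOT on Day 85 do.

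This rests on completers taking the last dose at the EOT visit within its window, on FU3 falling 12 weeks later within ±6 days, and on a 7-day week. How many completers fall on Day 85 as against Day 86 to 91 cannot be known from the documents.

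No primary or secondary endpoint result changes, because neither the duration nor the categories enter those analyses. It should still be corrected: the rule gives a wrong answer when followed, and the correction is small.

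**What to change.** Rewrite the SAP 7.7 paragraph to state:
- Duration of exposure (days) = last dose date − first dose date + 1, over the dosing period only, and say that this inclusive count is the day-count rule.
- Categories: 0 to 6 weeks (≤ 42 days), >6 to 12 weeks (43 to 84 days) and >12 weeks (≥ 85 days).
- Time in trial including follow-up goes on a separate line under its own label.

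With the inclusive count, every scheduled completer (85 to 91 days) falls in the top category, and a patient who stops on Day 84 stays in the middle one. A cut at ≥ 84 days combined with the + 1 would count that patient with the completers, so the rule and the cut must be set together. Giving the dosing period a name other than on-treatment, here and in SAP 7.3, would remove the double use of the term.

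The cost is one SAP paragraph and a small programming change. No new data are needed, since Protocol 6.2.3 already relies on the last intake date to schedule follow-up.

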7.8 SAFETY ANALYSIS

Safety analyses will be performed on the treated set (TS).

7.8.1 Adverse events

Unless otherwise specified, the analyses of AEs will be descriptive. All analyses of AEs will be based on the number of patients reporting an AE and not on the number of events. The reporting and analyses of AEs will follow the BI guideline for analyses and presentation of adverse event data (12). All AEs will be coded using the most current version of the Medical Dictionary for Drug Regulatory Activities (MedDRA) at the time of database lock. The intensity of AEs will be classified according to the Common Terminology Criteria for Adverse Events (CTCAE) version 4.03.

For analysis, multiple AE occurrences will be collapsed into one event if all of the following conditions apply:

- All AE attributes are identical (LLT, intensity, action taken, therapy required, seriousness, reason for seriousness, relationship, outcome, AE of special interest).
- Reported occurrences are time-overlapping or time-adjacent, where time-adjacency of 2 occurrences exists if the second occurrence started on the same day or on the day after the end of the first occurrence.

The analyses of AEs will be based on the concept of treatment emergent adverse events. Consistent with the REP definition provided in [Section 6.1](#), all AEs with onset dates between the date of first treatment administration and date of last follow-up will be assigned to the randomized treatment. All AEs occurring before first treatment administration will be assigned to screening. For details on the treatment definition, see [Section 6.1](#).

According to ICH E3 ([13](#)), AEs classified as ‘other significant’ need to be reported and will include those non-serious and non-significant adverse events with (i) ‘action taken = discontinuation’ or ‘action taken = reduced’, or (ii) marked hematological and other lab abnormalities or which lead to significant concomitant therapy as identified by the Clinical Monitor/Investigator at an MQRM.

An overall summary of AEs will be presented. This summary will include the following event categories:

- All AEs
- Drug-related AEs
- AEs leading to treatment discontinuation
- Serious AEs (SAEs)
- AESI
- Highest CTC grade
- Ocular AEs

The frequency and percentage of patients with AEs will be summarized by treatment, primary system organ class (SOC), and preferred term (PT) in each of the following tables:

- All AEs
- Drug-related AEs
- AEs leading to treatment discontinuation
- Drug-related AEs leading to treatment discontinuation
- SAEs
- Drug-related SAEs
- AEs leading to death
- AEs of special interest (AESI)
- Other significant AEs according to ICH E3 ([13](#)).

Per CTP Section 5.2.6.1.4, AESIs for this trial are events of hepatic injury defined by an elevation of AST and/or ALT ≥ 3 fold upper limit of normal (ULN) combined with an elevation of bilirubin ≥ 2 fold ULN measured in the same blood draw, or aminotransferase (ALT and/or AST) elevations ≥ 10 fold ULN. AEs related to these definitions will be summarized as AESIs.

Additionally, a table summarizing time to first AE from date of first dose of study drug will be presented by treatment arm, SOC and preferred term.

Primary endpoint: Ocular AEs

In addition to standard adverse event tables, separate summaries will be provided to address the primary endpoint and secondary safety endpoints. The frequency and percentage of patients reporting ocular AEs, as identified by the investigator as an ocular event on the AE eCRF, will be summarized by treatment, highest CTC grade, primary SOC, and PT for the primary endpoint analysis. The number and percentage of patients in each treatment arm

reporting specific ocular symptoms will be summarized and will be displayed by associated event in a listing. Additional summaries of serious ocular AEs, drug-related ocular AEs, serious drug-related ocular AEs, and ocular AEs leading to discontinuation will be provided, if any such events are reported. A Kaplan-Meier plot displaying time to first ocular event following first dose of study drug will be provided.

To assess the impact of the COVID-19 pandemic on this trial, adverse events reported after 01MAR2020 in the subset of patients active in the trial as of 01MAR2020 will be reported and listed in the CTR. Overall summaries of the subset of all AEs and subset of ocular AEs with start dates prior to 01MAR2020 will be reported separately. In addition, frequencies of AEs reported during the follow-up period will be reported in the subset of patients who completed the trial prior to 01MAR2020 and in the subset of patients who completed the trial after 01MAR2020.

Secondary endpoint: Non-ocular AEs

A separate set of the tables specified above for ocular AEs will be generated to summarize patients reporting AEs not identified as ocular AEs. These summaries will address the analysis of the secondary safety endpoint. The data will be summarized by treatment, MedDRA primary SOC, and PT.

For further details on the summarization of AE data, refer to BI guidelines ([5,12](#)).

7.8.2 Laboratory data

The analyses of laboratory data [REDACTED] will be descriptive in nature and will be based on BI standards ([6](#)).

For continuous safety laboratory parameters, standardized and normalized values will be derived as well as the differences from baseline. The process of standardization and normalization as well as standard analyses for safety laboratory data are described in the BI guidance for the display and analysis of laboratory data ([6](#)).

Laboratory values will be compared to their reference ranges and frequency tables will be provided for the number of patients within and outside the reference ranges at baseline, the last measurement on treatment and the last post-treatment follow-up. Descriptive statistics will be provided by treatment group for baseline, on-treatment values, values collected during follow-up visits and for changes from baseline. Frequency tables will summarize the number of patients with potentially clinically significant abnormalities as defined for the XLAB macro.

The Estimated Glomerular filtration rate as assessed by the CKD-EPI formula is calculated as:

$$\text{eGFR (ml/min/1.73 m}^2\text{)} = 141 * \min(\text{SCr}/\kappa, 1)^\alpha * \max(\text{SCr}/\kappa, 1) - 1.209 * 0.993 \text{Age} * 1.018 \text{ [if female]} * 1.159 \text{ [if black]}$$

where SCr is serum creatinine in mg/dL, κ is 0.7 for females and 0.9 for males, α is -0.329 for females and -0.411 for males, min indicates the minimum of SCr/κ or 1, and max indicates the maximum of SCr/κ or 1. The process of standardization and normalization as described in the guidance document (6) does not apply. Additionally, the shift tables for eGFR will use the following categories (similar to the staging of renal impairment): $eGFR \geq 90$; $60- < 90$; $30- < 60$; and < 30 .

Clinically relevant findings in laboratory data will be reported as AEs and will be analyzed as part of AE analyses.

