Laboratory data will be analyzed both quantitatively as well as qualitatively. The latter will be done via comparison of laboratory data to their reference ranges. Values outside the reference range as well as values defined as clinically relevant will be summarized. Treatment groups will be compared descriptively with regard to distribution parameters as well as with regard to frequency and percentage of patients with abnormal values or clinically relevant abnormal values.

Clinically relevant ECG findings will be reported as baseline conditions or AEs. Quantitative and qualitative ECG data from the ECG reading center will be reported descriptively.

Vital signs, physical examinations, or other safety-relevant data observed at screening, baseline, during the course of the trial and at the end-of-trial evaluation will be assessed with regard to possible changes compared to findings before start of treatment.

[REDACTED]

[REDACTED]

[REDACTED]

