6.7 BASELINE, TIME WINDOWS AND CALCULATED VISITS

Study day will be calculated relative to the date of the first dose of the randomized treatment. The day prior to the date of the first administration of randomized treatment will be Day -1 and the date of the first administration of randomized treatment will be Day 1. Day 0 will not exist.

Unless otherwise specified, baseline is defined as the last measurement collected on or prior to the date and time of first treatment administration. If no measurements are collected for a particular variable on or before the date of first treatment administration, no baseline value will be derived for that particular variable. Per the CTP, for the ophthalmic endpoints, baseline is defined as the value at Visit 2a; if not measured at Visit 2a then baseline is the value at Visit 1.

To utilize all available data, including values collected between protocol-specified visit windows, the time intervals and descriptions shown in [Table 6.7: 1](#) will be used in the analysis of safety and efficacy data with the following exceptions. Adverse events and concomitant medications are also collected during phone visits 2b (Study Day 8 ± 1) and 4b (Study Day 83 ± 1). Sites in Spain have additional mandatory visits 3c and 4c during which AEs, concomitant medications, vital signs and laboratory data are collected. Separate interval mapping will be defined in [Table 6.7: 2](#) and [Table 6.7: 3](#), respectively, to accommodate these exceptions.

If multiple values are recorded within a visit interval, the value collected closest to the planned visit date will be included in analyses of efficacy endpoints and vital signs data. For all other safety data, the worst of multiple values within an analysis window will be selected for analysis (see guidance for Handling, Display and Analysis of Laboratory Data [\(6\)](#)). Only one observation per time window will be selected for analysis at an on-treatment visit.

Table 6.7: 1 Visit intervals for efficacy endpoints

		Interval Definition		
Visit	Planned day	From (day)	To (day)	Visit description
1	-28 to -3	NA	-1	Screening
2	1	1	1 ^b	Baseline ^c
3	29	2	43	Week 4
4a	57	44	71	Week 8
EOT	85	72	Date of drug intake at EoT visit + 14	Week 12
FU1	EOT +28	Date of drug intake at EOT visit + 15	Date of drug intake in EOT visit +34	Follow-up 1
FU2	EOT +56	Date of drug intake in EOT visit +35	Date of drug intake in EOT visit +62	Follow-up 2

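### The laboratory reference-range table in SAP 7.8.2 uses only the last treatment-period value; an any-time on-drug count would be a cheap, minor improvement

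*SAP*

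**What the plan says.** Protocol 7.3.4 says that values outside the reference range and clinically relevant values will both be summarised. It compares the arms on the "frequency and percentage of patients with abnormal values or clinically relevant abnormal values". It names no time point.

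SAP 7.8.2 puts this into effect as follows:

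- **Reference-range table.** The section states that "frequency tables will be provided for the number of patients within and outside the reference ranges at baseline, the last measurement on treatment". The sentence then adds a third point, so that the two counted after baseline are "the last measurement on treatment and the last post-treatment follow-up".
- **Second frequency table.** "Frequency tables will summarize the number of patients with potentially clinically significant abnormalities as defined for the XLAB macro". The limits and the time rule of that macro are not given.
- **Summary statistics.** "Descriptive statistics will be provided by treatment group for baseline, on-treatment values, values collected during follow-up visits and for changes from baseline".
- **Adverse events.** "Clinically relevant findings in laboratory data will be reported as AEs and will be analyzed as part of AE analyses".
- **Outside source.** The "standard analyses for safety laboratory data are described in the BI guidance for the display and analysis of laboratory data", which is not among the documents.
- **eGFR.** Shift tables use four categories (90 or more, 60 to below 90, 30 to below 60, below 30). The section does not say which on-treatment value is used.

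SAP 6.7 adds that, for safety data other than vital signs, "the worst of multiple values within an analysis window will be selected for analysis".

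**The concern.** Safety and tolerability are the trial's primary objective (protocol synopsis and 7.1). Laboratory changes that appear early and then settle, for example in liver enzymes, creatinine or blood counts, are one pattern that the safety tables should be able to show by arm. A table built on the last value shows what is still abnormal at the end of treatment, not how many patients became abnormal. If such changes were more frequent on active drug, that difference would be reduced in this table.

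The SAP already uses an any-time principle in another safety domain: SAP 6.6 bases the new-onset QTc and QT categories on the maximum on-treatment interval. No such rule is stated for the laboratory reference ranges.

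**Working it through.** The documents give no figure for laboratory abnormality counts, so there is none to reproduce. The check is a comparison of the texts, followed by an illustration of size.

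**1. Which values exist.** The protocol Flow Chart schedules chemistry, hematology and urinalysis after the first dose at Visits 3, 4a and EOT (Weeks 4, 8 and 12), then at three follow-up visits. Sites in Spain have extra laboratory visits (SAP 6.7, Table 6.7: 3).

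**2. Which values the reference-range table uses.** It uses one treatment-period value. For a completer that is Week 12, so two of the three scheduled on-drug samples are left out.

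**3. Whether the worst-value rule closes the gap.** It does not. The rule picks the worst value inside one window, and Table 6.7: 2 makes Weeks 4, 8 and 12 separate windows.

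**4. Where a resolved Week 4 out-of-range value appears.**

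| Stated output | Is it there? |
|---|---|
| Reference-range table | No, if the last value is normal |
| Potentially clinically significant table | Only if it meets the macro's limits; no last-value limit is stated |
| AE tables | Only if judged clinically relevant |
| Summary statistics (SAP 7 includes minimum and maximum) | In the distribution, but not as a count of patients |
| Individual data listings (SAP 7) | Yes, but not as a by-arm count |

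**5. Which value counts as last.** SAP 6.1 runs the on-treatment period from first dose to the patient's end of trial. SAP 7.8.2 separates the last value on treatment from the last follow-up, and SAP 7.3 uses on-treatment for Visits 3, 4 and EOT. Read literally with SAP 6.1, the last on-treatment value could be a follow-up value.

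**6. Illustration of size.** Inputs: 50 patients per arm (protocol 7.7) and three on-drug visits. The per-visit out-of-range rate p and the between-visit correlation are assumptions.

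- Expected count in the last-value table: 50 × p.
- Expected count ever out of range, independent visits: 50 × [1 − (1 − p)³]. For p = 5% this is 50 × (1 − 0.95³) = 50 × 0.143 = 7.1, against 50 × 0.05 = 2.5.
- Correlated visits: a trivariate normal with a common correlation and the cut-off set so that each visit has rate p.
- Share missed: 1 − p / P(ever out of range). For p = 5% and independent visits: 1 − 0.05/0.143 = 65%.

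| p | Correlation | Last value, of 50 | Any visit, of 50 | Share missed |
|---|---|---|---|---|
| 2% | 0 | 1.0 | 2.9 | 66% |
| 2% | 0.5 | 1.0 | 2.5 | 61% |
| 2% | 0.8 | 1.0 | 2.0 | 50% |
| 5% | 0 | 2.5 | 7.1 | 65% |
| 5% | 0.5 | 2.5 | 5.9 | 58% |
| 5% | 0.8 | 2.5 | 4.6 | 46% |
| 20% | 0 | 10.0 | 24.4 | 59% |
| 20% | 0.5 | 10.0 | 19.4 | 49% |
| 20% | 0.8 | 10.0 | 15.7 | 36% |

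**7. The same question by persistence.** An abnormality present at exactly one of the three visits, equally likely at each, is shown with probability 1/3. One lasting two consecutive visits is shown in 1/2 of cases if it starts at Week 4 or Week 8 with equal chance, and in 2/3 if a start at Week 12 is also allowed. One that lasts to the end of treatment is always shown.

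**The case against.** Much of the opposing case stands.

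- **Abnormalities at Week 4 or 8 are not lost altogether.** A reader might infer that they go uncounted. The documents do not support that: the potentially clinically significant table has no stated last-value limit, clinically relevant findings enter the AE tables, and hepatic injury is an AE of special interest at any blood draw. What remains is lesser out-of-range values that resolve.
- **The protocol is not contradicted.** Protocol 7.3.4 gives no time point, so a last-value table together with a clinically-significant table is a permissible, if narrow, reading.
- **The macro's limits are unknown.** One might argue that its table cannot fill the gap because its limits are wider than the reference range. The documents give neither the limits nor the time rule, so that argument is not available.
- **The sponsor guidance may already require any-time or by-visit counts.** This cannot be checked. It is a reason for the SAP to state the rule, not proof of a missing analysis.
- **eGFR.** One might infer that the shift table uses the last value, so that a patient going 75, 52, 55, 63 would show no shift. The SAP does not say this; it leaves the choice open.
- **The size depends on the assumptions.** As the correlation approaches 1, the share missed falls to zero. An abnormality that leads to early stopping would usually be the last on-drug value and so be counted, because Table 6.7: 2 starts follow-up one day after the last dose in that case.
- **Noise.** The trial is exploratory, and a worst-value table over many analytes collects more chance findings. That is a fair reason to keep the last-value columns, but not a reason to have only those.

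**Conclusion.** The point holds in a limited form. In the stated text, the only patient count against the reference ranges takes one treatment-period value, so for completers the Week 4 and Week 8 results do not enter it. The gap is a by-arm, any-time count of out-of-range values that are neither potentially clinically significant nor reported as AEs.

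For rates of 2% to 20% and correlations of 0 to 0.8, the table misses about 36% to 66% of patients ever out of range. These inputs are assumptions, so the range shows the direction and possible size of the undercount and is not an estimate for this trial.

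This is a cheap improvement of minor severity. It does not affect the primary endpoint or either secondary endpoint analysis.

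**What to change.** In SAP 7.8.2:

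1. Add reference-range counts by arm from baseline to the lowest and from baseline to the highest value between first and last dose, including unscheduled values.
2. Keep the last on-drug value and the last follow-up value as further columns, to show recovery.
3. State that the eGFR shift table uses the lowest on-drug value.
4. Define the last measurement on treatment as ending with the drug-intake period, so that the SAP 6.1 definition does not extend it into follow-up.

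If the sponsor guidance already provides any-time counts, one sentence saying so would meet item 1.

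The cost is SAP wording and, for each parameter, a lowest and a highest on-drug value derived from data already collected. The downside is more chance out-of-range counts, in both arms, because each patient has three or more chances to be counted. The by-arm comparison and the retained last-value columns help the reader to allow for this.
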